12.5.4. Safety

Adverse Events of Special Interest

 • Section 8.2: Adverse Events of Special Interest Analyses provides a full list of AEs of special interest for this compound. AESIs of anaphylaxis reactions, systemic reactions, and local injection site reactions are collected via targeted eCRF. • The AESIs of opportunistic infections, malignancies, serious CVT events and serious ischemic events will be identified from a list of relevant preferred terms maintained within a project level reference dataset; created based on the latest version of the MedDRA dictionary available at the time of database freeze for this study (See Program Safety Analysis Plan for additional details).
Laboratory Parameters

 • If a laboratory value which is expected to have a numeric value for summary purposes, has a non-detectable level reported in the database, where the numeric value is missing, but typically a character value starting with '<x' or '>x' (or indicated as less than x or greater than x in the comment field) is present, the number of significant digits in the observed values will be used to determine how much to add or subtract in order to impute the corresponding numeric value. 
 ○ Example 1: 2 Decimal Points = '< x' becomes $x - 0.01$ ○ Example 2: 1 Decimal Point = '> x' becomes $x + 0.1$ ○ Example 3: 0 Decimal Points = '< x' becomes $x - 1$
Immunogenicity (Binding Antibody Assay Results)

 • Positive binding antibody assay results are to be categorised as transient positive or persistent positive accordingly to the following definitions: • For all post-baseline visits, other than final study assessment 
 ○ Transient positive = a single positive immunogenic response at a visit, where the previous visit was negative ○ Persistent positive = a positive immunogenic response at a visit, where the previous visit was also positive • For the final assessment: 
 • Any positive response will be considered a persistent response, regardless of the status at the previous visit

12.5.5. Pharmacokinetic

There will be no derivation of Pharmacokinetic Parameters for this study.

12.5.6. Pharmacodynamic and Biomarker

Pharmacodynamic
Blood Eosinophils

 • Blood eosinophil counts will be log transformed (loge) prior to analysis. • For the log transformation values of 0 GI/L will be imputed to a value of minimum for all non-missing results/2.

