In the previous phase 2 study of mepolizumab in subjects with moderate AD (Study SB240563/045), the median blood eosinophil count decreased from 432.5 to 88.5 cells/ μ L in the mepolizumab group and increased from 495 to 605 cells/ μ L in the placebo group from Day 0 to Day 14. Acknowledging the uncertainty around the true mean baseline blood eosinophil count in the targeted population in the absence of concurrent therapy, an assumed geometric mean baseline of 500 to 800 cells/ μ L was considered reasonable. Based on the established mepolizumab dose-response for blood eosinophil reduction, for such a geometric mean baseline range, a reduction to a predicted geometric mean absolute blood eosinophil count of 100 to 150 cells/ μ L would be anticipated with a 100 mg SC dose administered every 4 weeks [GlaxoSmithKline Document Number [2015N238375_00](#), 2015]. Based on the results of studies in other diseases (e.g., asthma), this magnitude of decrease in blood eosinophil level is anticipated to be therapeutic in moderate to severe AD subjects.

This study utilizes a Treatment Period of 16 weeks with study treatment administered at the Baseline visit, Week 4, Week 8, and Week 12. For those subjects randomized to mepolizumab, four doses will provide therapeutic coverage to Week 16. A 16-week Treatment Period is expected to be sufficient to reduce eosinophils in the skin and to assess clinical disease response to study treatment.

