10.1.2. Summary Measure

- Geometric Means for ratio to baseline in blood eosinophil counts and for absolute blood eosinophil count at each visit.
- Only listings will be presented for biomarker endpoints.

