10.1.4.1. Statistical Methodology Specification

Endpoint

 Ratio to baseline blood eosinophil counts (Note: from standard haematology assessments)
Model Specification

 Mixed Models Repeated Measures (MMRM) analysis. The analysis will include all measurements at scheduled visits Terms in the model: Response: Ratio to Baseline Blood eosinophil count (\log_e transformed prior to analysis) (see Appendix 5: Derived and Transformed Data, Section 12.5.6). 
 Categorical: Treatment group, Visit. Continuous/covariate: Baseline blood eosinophil count. Interaction: Treatment group*Visit. Repeated: Visit. The Kenward and Roger method for approximating the denominator degrees of freedom and correcting for bias in the estimated variance-covariance of the fixed effects will be used. An unstructured covariance structure for the R matrix will be used by specifying 'type=UN' on the REPEATED line.
Model Checking

 Distributional assumptions underlying the model used for analysis will be examined by obtaining a normal probability plot of the residuals and a plot of the residuals versus the fitted values (i.e. checking the normality assumption and constant variance assumption of the model respectively) to gain confidence that the model assumptions are reasonable.
Model Results Presentation

 The results of the analysis from the MMRM model will be presented for each visit as LS Geometric Mean (SE), LS Geometric Mean Ratio to Baseline (95% Confidence Interval) for each treatment group, Geometric Treatment Ratio (Mepolizumab/Placebo) and corresponding 95% Confidence Interval.
Sensitivity and Supportive Analyses

 There are no planned sensitivity or supportive analyses.

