 Any time post baseline would be Positive for a participant who had both Negative and Positive post baseline results.

Example: SAF_T5
 Protocol: 205050
 Population: Safety

Table 3.40

Summary of Binding Antibody Assay Results: Highest Treatment Emergent Confirmatory Result
 Any Time Post Baseline

Assay Result	Placebo (N=xx)	Mepolizumab 100 mg SC (N=xx)
n	xx	xx
Negative	xx (xx%)	xx (xx%)
Positive	xx (xx%)	xx (xx%)
Transient Positive	xx (xx%)	xx (xx%)
Persistent Positive	xx (xx%)	xx (xx%)
Titer Value		
Median	32.0	32.0
Min.	32	32
Max.	32	32

Note: Includes only results from subjects who do not have a positive ADA assay prior to the first dose of investigational product.

Example: PD_T1
 Protocol: 205050
 Population: Intent-to-Treat

Table 5.1
 Summary of Blood Eosinophil Count at Each Visit

Visit			Placebo SC (N=68)	Mepolizumab 100 mg SC (N=68)
Baseline	Blood Eosinophils (10 ⁹ /L)	n	68	68
		Geo Mean	0.172	0.177
		Std Logs	1.3522	1.2890
		Median	0.215	0.190
		Min.	0.00	0.01
		Max.	4.45	6.72
Week 4	Blood Eosinophils (10 ⁹ /L)	n	66	66
		Geo Mean	0.141	0.035
		Std Logs	1.4972	0.9999
		Median	0.195	0.040
		Min.	0.00	0.00
		Max.	3.35	1.56
	Blood Eosinophils Ratio to Baseline	n	66	66
		Geo Mean	0.796	0.189
		Std Logs	1.2976	1.1936
		Median	0.964	0.185
		Min.	0.00	0.00
		Max.	22.00	4.00

Note: Data were log transformed.

Note: Where a result of zero was recorded, a small value (i.e. minimum all non-missing results/2) was added prior to log transformation

Example: PD_T2
 Protocol: 205050
 Population: Safety

Table 5.2
 Summary of Mixed Model Repeated Measures (MMRM) Analysis for Blood Eosinophils Count

Visit	Statistic	Placebo SC N=xx	Mepolizumab 100 mg SC N=xx
Week 4	n	xx	xx
	LS Geometric Mean (SE)	x.xx (xx.xxx)	x.xx (xx.xxx)
	LS Geometric Mean Ratio to Baseline (SE)	x.xx (xx.xxx)	x.xx (xx.xxx)
	95% Confidence Interval	(x.xx, x.xx)	(x.xx, x.xx)
	Treatment Ratio		x.xx
	95% Confidence Interval		(x.xx, x.xx)
Week 8	n	xx	xx
	LS Geometric Mean (SE)	x.xx (xx.xxx)	x.xx (xx.xxx)
	LS Geometric Mean Ratio to Baseline (SE)	x.xx (xx.xxx)	x.xx (xx.xxx)
	95% Confidence Interval	(x.xx, x.xx)	(x.xx, x.xx)
	Treatment Ratio		x.xx
	95% Confidence Interval		(x.xx, x.xx)

Note: Treatment Ratio (Mepolizumab/Placebo) and 95% Confidence Intervals for Ratio to Placebo are obtained from MMRM model, with fixed categorical effects of Treatment, Visit, and Treatment-By-Visit Interaction and fixed continuous covariates of Baseline. 'XX' covariance structure was used.

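### The SAP's rule for zero eosinophil counts returns zero whenever it is needed, because the minimum it halves is not restricted to non-zero results

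*SAP*

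**What the plan says.** SAP 12.5.6: "Blood eosinophil counts will be log transformed (loge) prior to analysis". For that transformation, "values of 0 GI/L will be imputed to a value of minimum for all non-missing results/2".

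SAP Appendix 10, footnote to shell PD_T1 (Table 5.1): "Where a result of zero was recorded, a small value (i.e. minimum all non-missing results/2) was added prior to log transformation".

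SAP 12.6.2 treats data as missing when they were requested but not provided, so that the field is blank. A recorded 0 is not blank.

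The transformed counts feed Table 5.1 (geometric means by visit), Table 5.2 and Figure 5.2. The model behind the last two, in SAP 10.1.4.1, is a "Mixed Models Repeated Measures (MMRM) analysis" of the log ratio to baseline, with the instruction that "The analysis will include all measurements at scheduled visits". It is the only pharmacodynamic model in the SAP. For the other markers, SAP 10.1.2 states: "Only listings will be presented for biomarker endpoints".

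**The concern.** The rule exists so that zeros can be logged, and as worded it does not do that. Neither place restricts the minimum to positive values. Neither says whether it is taken over all visits and both arms.

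If the formula is coded as it stands, the substituted value is still zero and the log cannot be formed. The record then has no usable response and drops out of the visit's geometric mean and of the model. The records lost are the lowest counts. Entry requires at least 350 cells/µL at Screening and mepolizumab lowers eosinophils, so zeros would be expected mainly after dosing on the active arm. Losing them raises the active-arm geometric mean and moves the treatment ratio towards 1. A repeated-measures model may recover part of this from the subject's other visits. It does not remove the problem, because a record would be missing on account of its own unanalysed value.

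**Working it through.** **Inputs from the documents**
- Substitution formula: SAP 12.5.6 and the PD_T1 footnote.
- Expected level on treatment: Protocol 4.5 anticipates a "reduction to a predicted geometric mean absolute blood eosinophil count of 100 to 150" cells/µL, that is 0.10 to 0.15 GI/L.
- Post-dose visits with haematology: Weeks 4, 8, 12, 16 and 20.
- Planned size: about 56 randomised, so about 28 per arm. The study stopped after an interim analysis at about half of that, or about 14 per arm.
- Shell PD_T1, Week 4, mepolizumab: n 66, geometric mean 0.035, SD of logs 0.9999, minimum 0.00. These are placeholders (the shell shows N=68 per arm), not forecasts.

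**Assumptions not in the documents:** lognormal counts; results reported to two decimals in GI/L, so that anything under 5 cells/µL is recorded as 0.00; smallest non-zero result 0.01, so the intended substitute is 0.005; SD of logs 0.7 to 1.3; 14 to 28 active subjects at a visit. The plan gives no figure of its own to reproduce.

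**Step 1: does the rule work?** Take the made-up results {0, 0, 0.01, 0.02, 0.04, 0.05, 0.08, 0.15}.
- As written: minimum 0, substitute 0/2 = 0, log undefined. Six of 8 values are usable, with geometric mean 0.041.
- With the minimum over non-zero results: substitute 0.01/2 = 0.005. All 8 are usable, with geometric mean 0.024.

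**Step 2: how many zeros, and what does dropping them do?** Zero share f = Φ(ln(5/GM)/SD), where GM is the geometric mean in cells/µL. The ratio of the geometric mean with zeros dropped to that with zeros set to 0.005 is (G/0.005)^f, where G is the non-zero geometric mean in GI/L.

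| GM (cells/µL) | SD of logs | ln(5/GM)/SD | Zero share f | Dropped ÷ imputed |
|---|---|---|---|---|
| 100 | 0.7 | −4.28 | 0.001% | 1.000 |
| 100 | 1.0 | −3.00 | 0.14% | 1.004* |
| 100 | 1.3 | −2.30 | 1.06% | 1.033* |
| 150 | 0.7 | −4.86 | <0.001% | 1.000 |
| 150 | 1.0 | −3.40 | 0.03% | 1.001* |
| 150 | 1.3 | −2.62 | 0.44% | 1.015 |
| 35 (shell placeholder) | 1.0 | −1.95 | 2.6% | 1.053* |

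*From 1,000,000 simulated counts rounded to 0.01 GI/L. The rest use the formula with G ≈ GM; for example 30^0.0044 = 1.015.

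Reporting precision matters more than the other inputs. With one decimal, a zero would be any count under 50 cells/µL, and at 100 to 150 cells/µL the zero share becomes 6% to 30% over the same range of SDs.

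**Step 3: one zero at one visit.** The averages above hide what a single lost record does in a small arm. With n subjects, one of them at zero and the others averaging G, the geometric mean with the zero kept is (0.005/G)^(1/n) times the value with it dropped.
- G = 0.10, n = 14: 0.05^(1/14) = 0.81, or 19% lower.
- G = 0.10, n = 28: 0.05^(1/28) = 0.90, or 10% lower.
- G = 0.04, n = 14 and 28: 0.125^(1/14) = 0.86 and 0.125^(1/28) = 0.93, or 14% and 7% lower.

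**Step 4: chance that the rule is called at all.** This is 1 − (1 − f)^m for m active-arm post-dose records, treating records as independent. At GM 100 and SD 1.0 it is 9% for m = 14 × 5 = 70 and 18% for m = 28 × 5 = 140. At SD 1.3 it is 53% and 78%.

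**A second source of zeros.** SAP 12.5.4 converts a two-decimal below-limit result by subtracting 0.01 from the limit. A result reported as <0.01 would become 0.01 − 0.01 = 0.00 and pass into the zero rule.

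**The case against.** The intent can be recovered. The footnote calls the substitute a small value, which zero is not. The shell shows a minimum of 0.00 beside finite geometric means, and the model is meant to use every scheduled measurement. A programmer whose substitute came out as zero would probably notice and use the smallest positive result. All of this stands, and it makes the defect one of wording. It does not supply the formula: both places state the same one, and it is wrong in both.

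Three stronger readings are tempting, and the documents do not support them.

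- A reader might infer that the SAP plans to discard zeros. It does not. Discarding would contradict "The analysis will include all measurements at scheduled visits" and would happen only through literal programming.
- A reader might infer that the most depleted subjects leave the analysis. The model repeats over visits, so a zero costs one visit record. A subject is lost only if the baseline is zero, which is unlikely given the entry threshold, or if every post-baseline value is zero.
- A reader might infer a large bias by supposing that 5% to 20% of active-arm values are zero. No document gives such shares. Under two-decimal reporting, a 5% share needs an SD of logs of ln(20)/1.645 = 1.82 at 100 cells/µL, or ln(30)/1.645 = 2.07 at 150. A 20% share needs ln(20)/0.842 = 3.56 or more. The shell's placeholder SD is 1.0.

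The stakes are also low. The endpoint is exploratory and no formal hypothesis testing is planned. Table 5.1 also reports the median, minimum and maximum, and individual counts appear in Figure 5.1 and Listing 36, so zeros would remain visible.

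**Conclusion.** The rule is wrong as written: it fails in the one case it was written for. If it were followed exactly, zero-count visit records would be lost from the geometric means and the eosinophil model, with a bias towards less apparent depletion on mepolizumab.

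The expected bias in the active-arm geometric mean is about 0 to 3% at the protocol's predicted level, given two-decimal reporting and an SD of logs of 0.7 to 1.3. It would be larger with deeper depletion (about 5% at the shell's placeholder values) or with coarser reporting. At a single visit, one lost zero is worth 10 to 19% of the raw geometric mean at 0.10 GI/L with 14 to 28 subjects; the model may recover part of that. No primary or secondary efficacy result is touched. This is a minor defect that should be corrected before programming.

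**What to change.** In SAP 12.5.6 and in the PD_T1 footnote, define the substitute as *half the smallest non-zero, non-missing result across all subjects and visits*. This also settles the scope of the minimum, which is now unstated.

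Check that the below-limit rule in SAP 12.5.4 does not turn a <0.01 eosinophil result into 0.00. If it does, say which of the two rules governs eosinophils.

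The cost is a few words in two places and one programming check. No data collection or other analysis changes.

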12.6. Appendix 6: Reporting Standards for Missing Data

12.6.1. Premature Withdrawals

Element	Reporting Detail
General	
 • Subject study completion (i.e. as specified in the protocol) was defined as if he/she receives all planned doses of study treatment and completes the Week 16 (Post-Treatment 1) and Week 20 (Post-Treatment 2) visits. • Withdrawn subjects were not replaced in the study. • All available data from participants who were withdrawn from the study will be listed and all available planned data will be included in summary tables and figures, unless otherwise specified. • Withdrawal visits will be slotted as per Appendix 2: Assessment Windows

12.6.2. Handling of Missing Data

Element	Reporting Detail
General	
 • Missing data occurs when any requested data is not provided, leading to blank fields on the collection instrument: 
 ○ These data will be indicated using a “blank” in subject listing displays. Unless all data for a specific visit are missing in which case the data is excluded from the table. ○ Answers such as “Not applicable” and “Not evaluable” are not considered to be missing data and should be displayed as such.
Outliers	
 • Any participants excluded from the summaries and/or statistical analyses will be documented along with the reason for exclusion in the clinical study report.

12.6.2.1. Handling of Missing and Partial Dates

Element	Reporting Detail
General	
 • Partial dates will be displayed as captured in subject listing displays.
Adverse Events	
 • The eCRF allows for the possibility of partial dates (i.e., only month and year) to be recorded for AE start and end dates; that is, the day of the month may be missing. In such a case, the following conventions will be applied for calculating the time to onset and the duration of the event: 
 ○ Missing Start Day: First of the month will be used unless this is before the start date of study treatment; in this case the study treatment start date will be used and hence the event is considered On-treatment as per Appendix 3: Study Phases and Treatment Emergent Adverse Events. ○ Missing Stop Day: Last day of the month will be used, unless this is after the stop date of study treatment; in this case the study treatment stop date will be used. • Completely missing start or end dates will remain missing, with no imputation applied. Consequently, time to onset and duration of such events will be missing.

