7.4.1.1. Time period and Frequency for collecting AE and SAE information

- Any SAEs assessed as related to study participation (e.g., protocol-mandated procedures, invasive tests, or change in existing therapy) or related to a GSK product will be recorded from the time a subject consents to participate in the study up to and including any follow-up contact.
- AEs will be collected from the start of Study Treatment until the follow-up contact (i.e., the Week 20 visit) (See Section [7.4.1.3](#)), at the timepoints specified in the Time and Events Table (Section [7.1](#)).
- Medical occurrences that begin prior to the start of study treatment but after obtaining informed consent may be recorded on the Medical History/Current Medical Conditions section of the CRF.
- All SAEs will be recorded and reported to GSK within 24 hours, as indicated in [Appendix 11](#).

- Investigators are not obligated to actively seek AEs or SAEs in former study subjects. However, if the investigator learns of any SAE, including a death, at any time after a subject has been discharged from the study, and he/she considers the event reasonably related to the study treatment or study participation, the investigator must promptly notify GSK.

NOTE: The method of recording, evaluating and assessing causality of AEs and SAEs plus procedures for completing and transmitting SAE reports to GSK are provided in [Appendix 11](#).

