9.4.2. Secondary Analyses

The secondary efficacy endpoints are defined in Section 3.

IGA: Subjects' change from baseline in IGA score and the proportion of subjects with a 2-point decrease from baseline will be summarized by visit. Point-estimates and 90% confidence intervals for the differences between the experimental and vehicle arm at Week 16 will be presented. No formal hypothesis testing will be performed.

EASI: Subject's change from baseline/percent change from baseline will be summarized by visit. Point-estimates and 90% confidence intervals for the differences between the experimental and vehicle arm at Week 16 will be presented. No formal hypothesis testing will be performed.

Continuous endpoints will be presented as means and 90% confidence intervals.

Safety Analyses

AEs will be coded using the MedDRA coding dictionary and summarized by preferred term and treatment group. SAEs occurring pre-treatment and AEs and SAEs occurring during active treatment and post-treatment will be summarized separately. Separate summaries will be provided for all AEs, investigational product-related AEs, SAEs, AEs of special interest (including systemic reactions [allergic/type I hypersensitivity or Systemic Other] and local injection site reactions) and for AEs leading to permanent discontinuation of investigational product or withdrawal from the study. All laboratory parameters for clinical chemistry and hematology will be summarized and tabulated.

Summary statistics of pulse rate and systolic and diastolic blood pressure will be presented by visit.

Immunogenicity will be summarized using appropriate descriptive statistics.

Full details of planned analyses of safety endpoints will be included in the RAP.

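### The SAP's rule for a missing start day counts every such SAE between consent and first dose as on-treatment, even when its recorded month or stop date proves it came earlier

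*SAP*

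**What the plan says.** SAP 12.6.2.1 notes that the eCRF accepts adverse event dates with month and year only. For a missing start day it says "First of the month will be used unless this is before the start date of study treatment". When the first of the month does fall before first dose, "in this case the study treatment start date will be used and hence the event is considered On-treatment as per Appendix 3". For a missing stop day it says "Last day of the month will be used, unless this is after the stop date of study treatment", in which case the treatment stop date is used. Dates with nothing recorded are left alone: "Completely missing start or end dates will remain missing, with no imputation applied".

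Three other places bear on this:

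- Protocol 7.4.1.1 says that SAEs judged related to taking part in the study or to a sponsor product "will be recorded from the time a subject consents to participate in the study up to and including any follow-up contact". Non-serious events are collected only once treatment has started.
- SAP 12.3.1 defines a pre-treatment phase as any date before the first dose.
- Protocol 9.4.2 says that "SAEs occurring pre-treatment and AEs and SAEs occurring during active treatment and post-treatment will be summarized separately".

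**The concern.** The usual reason for substituting the first-dose date is that an event recorded in the month of first dose might have begun on either side of it, and the cautious choice is to count it as on-treatment. The SAP rule reaches further. It compares only the first of the recorded month with first dose, so it also fires for any earlier month, where month and year alone settle that the event was pre-treatment. It does not consult the stop date either, so an event known to have ended before first dose is moved as well.

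At stake is a serious event appearing in the on-treatment tables (SAP Tables 3.1 and 3.6) although the database shows that it preceded treatment. That conflicts with the SAP's own phase definition and with the protocol's separation of pre-treatment SAEs. A start date later than the stop date is a further visible error.

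**Working it through.** The plan gives no figure on this point, so the check applies the rule as written.

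**Does the rule ever return pre-treatment?** Let F be the first-dose date, T the true onset and M the first day of the month of T. Always M ≤ T. If T < F, then M < F, the condition is met and the imputed start is F. SAP 12.3.1 classes F as on-treatment. So every event with a true onset before first dose and a missing start day becomes on-treatment. No other rule reverses this: the notes to the treatment-emergent flag in SAP 12.3.2 address a missing treatment stop date and times of day, not partial event dates.

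**Can such records exist?** Related SAEs are collected from consent. Under Protocol 4.2, pre-screening takes up to 4 weeks and screening 1 to 2 weeks, so ordinarily up to 4 + 2 = 6 weeks. Subjects stopping a biologic may take up to 20 weeks. Either span can cross a month boundary. The subject must go on to be dosed, since the tables use the Safety population.

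**Worked dates** (illustrative; first dose 15 August 2017). Duration is taken as stop − start + 1, which is an assumption because the SAP gives no formula for it.

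| Recorded start | Stop | Imputed start | Duration |
|---|---|---|---|
| July 2017 | 20 July | 15 August | −26 + 1 = −25 days |
| July 2017 | July, imputed as 31 July | 15 August | −15 + 1 = −14 days |
| August 2017 | 10 August | 15 August | −5 + 1 = −4 days |
| August 2017 | 20 August | 15 August | 5 + 1 = 6 days |

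The first three rows are provably pre-treatment and come out on-treatment with the dates reversed. The fourth is ambiguous, and there the SAP's choice is reasonable.

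**How often would dates be reversed?** The rule was applied to first doses on each day of 2017, with true onset 1 to L days before first dose and true duration of 1, 3, 7 or 14 days, all equally weighted. The lengths are L = 2 × 7 = 14, 6 × 7 = 42 and 20 × 7 = 140 days. These inputs are assumptions, not trial data.

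| L (days) | Classed on-treatment, SAP rule | Stop before start, complete stop date | Stop before start, partial stop date | Classed on-treatment after the fix, complete stop date |
|---|---|---|---|---|
| 14 | 100% | 62.5% | 12.9% | 30.7% |
| 42 | 100% | 87.5% | 52.5% | 10.2% |
| 140 | 100% | 96.3% | 85.7% | 3.1% |

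With the fix and complete stop dates, no reversed dates remain. The events still classed on-treatment are those in the month of first dose that were continuing at first dose, where the data cannot settle the onset.

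**Size of one record.** Protocol 4.3 plans about 56 randomized subjects at 1:1, so 56 / 2 = 28 per arm, and 1 / 28 = 3.6 percentage points. The SAP reports that the study was stopped after an interim analysis at about half the planned subjects and does not give the final arm size. If it were half of 28, one subject would be 1 / 14 = 7.1 points.

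**The case against.** The case for leaving the rule alone has several parts.

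- **Exposure is narrow.** Before dosing only related SAEs are recorded. They go to the sponsor within 24 hours, and the investigator reviews the hospital and diagnostic records, so a missing onset day is unlikely. Nothing in the documents shows that such a record exists. This stands, and it is why the point is minor.
- **The convention is conservative.** It treats both arms alike and over-counts on-treatment events. That is a fair defence for the month of first dose. It does not justify overriding a month or stop date that was actually recorded.
- **The rule serves only time to onset and duration.** The SAP does introduce it that way: "the following conventions will be applied for calculating the time to onset and the duration of the event". But the same rule goes on to declare that the event is on-treatment, so it also decides the phase.
- **Listings keep partial dates as captured.** So the recorded month should remain visible in Listing 12. The summary tables would still be wrong, and would disagree with the listing.

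A reader might also infer more than the text supports. The rule does not move every event dated before first dose: complete dates are untouched and wholly missing dates stay missing. The 20-week period is not general; it applies to subjects stopping a biologic. A time to onset of zero cannot be asserted, because the SAP states no formula for it, and Tables 3.1 and 3.6 are not titled as showing onset or duration. Reversed dates are possible, not certain: they need a stop date before first dose, or a partial stop date in an earlier month.

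**Conclusion.** The rule is wrong as written, within a narrow scope: SAEs collected between consent and first dose, with month and year of onset known and the day missing, in subjects who were later dosed. For these it always returns on-treatment, including when the recorded month or stop date proves otherwise, and it can place the start after the stop.

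The number of affected records cannot be derived from the documents and is probably very small or zero. If one subject with no other on-treatment SAE were affected, that arm's rate would move by at least about 3.6 points. This is a lower bound, resting on at most about 28 subjects per arm; it is not a fixed figure for this trial, because the final arm size is not stated. The duration examples rest on an assumed formula, and the percentages for reversed dates on assumed onset times and event lengths. The classification result needs neither. This is a worthwhile clarification, and nothing here bears on the efficacy conclusions.

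**What to change.** Amend SAP 12.6.2.1 so that the first-dose date is imputed only when both conditions hold:

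1. the recorded month and year equal the month and year of first dose; and
2. no stop date, complete or imputed from a partial date, falls before first dose.

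In all other cases use the first of the recorded month. An event from an earlier month, or one in the month of first dose that had stopped before dosing, is then classed as pre-treatment. An event in the month of first dose that was still running at dosing, or has no stop date, keeps the present cautious treatment.

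Reclassified SAEs also need somewhere to be reported. The SAP display list has on-treatment and post-treatment SAE tables (3.6 and 3.7) but no pre-treatment one. Add a short pre-treatment SAE summary or listing to meet Protocol 9.4.2; otherwise these events would drop out of the phase-specific SAE tables.

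The cost is one extra sentence in the SAP, a small code change and one small display.
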